5.3 Description of Treatments

5.3.1 Investigational Product

FS VH S/D 500 s-apr is to be applied with cannula by dripping in a thin and continuous layer with a 5 mm overlap on each side of the sutured line, ensuring that all suture holes are covered ([Appendix 6](#)).

[REDACTED]

5.3.2 Control

The DuraSeal Dural Sealant is to be applied with the DuraSeal System Applicator by spraying a thin (1 – 2 mm) coating, ensuring that all suture holes are covered ([Appendix 7](#)).

5.3.3 Valsalva Manoeuvre

The Valsalva manoeuvre is to be performed by the anaesthesiologist to increase the intra-thoracic pressure (eg, by increasing the positive end-expiratory pressure or by giving a large tidal volume and hold the inflating pressure) to approximately 25 cm H₂O constantly for up to 5 - 10 seconds to transiently elevate the ICP and test for any CSF leaks.

5.3.4 Antibiotic Prophylaxis

All patients, regardless of treatment arm, will have peri-operative antibiotic prophylaxis, according to the guidelines at each site.

5.3.5 Rescue Therapy

In case of continuous CSF leak in spite of treatment (ie, treatment failure), rescue therapy using standard of care is permitted at the surgeon's choice (including use of other sealants, dural patches, etc. [excluding further use of the IP or control in either of the 2 groups]).

In case of rescue therapy, the choice of products must be captured in the eCRF (brand name of the material used for rescue therapy, application method, amount used).

5.4 Treatments Administered

Patients who are ≥ 18 years of age who have signed the ICF and who are eligible by intra-operative inclusion/exclusion criteria will undergo elective cranial surgery with durotomy of the PF or ST region with either craniotomy or craniectomy. The neurosurgical procedures are to be performed according to the standard practices applicable to each indication.

Treatments will be administered intra-operatively, during dural closure, and consist of sutures with FS VH S/D 500 s-apr or sutures with DuraSeal Dural Sealant.

5.4.1 Description of Treatment and Assessment of CSF Leak (Including Valsalva Manoeuvre)

Dura will be closed with sutures, needle sizes, and suturing techniques according to the surgeons' preference. Suture specification must be captured in the eCRF (type, size,

closure technique). Special care will be taken to ensure that if tenting sutures are used, they do not perforate the dura. Use of tenting sutures must be captured in the eCRF.

The surgeon will visually inspect the dural suture line for CSF leakage after application of the allocated treatment (FS VH S/D 500 s-apr or DuraSeal Dural Sealant) and after waiting at least 3 minutes if the treatment is FS VH S/D 500 s-apr. CSF leaks will be defined as any overt flow, seepage, weeping, or sweating of CSF through the dura suture line, regardless of volume. Patients who have a CSF leak, as defined by observing a spontaneous CSF leak or CSF leak after Valsalva manoeuvre (Section 5.3.3) after primary suturing will have their randomisation assignment (Section 5.5) applied.

If the suture line is watertight (ie, no CSF leak), then the suture line must be inspected again after applying the Valsalva manoeuvre (intrathoracic pressure increased to 25 cm H₂O for up to 5 - 10 seconds; Section 5.3.3). If the suture line after the Valsalva manoeuvre is watertight, the treatment is deemed a success, ie, intra-operative CSF leak free.

Note: After the end of the surgical intervention of the brain, physiologic liquids (eg, physiological saline) are to be used to prevent any pneumocephalus and to ensure evaluation of the primary endpoint (no intra-operative CSF leakage and 30 (\pm 3)-day post-operative CSF leakage).

5.5 Method of Assigning Patients to Treatment Groups

The patient will be randomised in a 1:1 allocation ratio stratified by center and surgical regions (PF or ST) to 1 of 2 treatment arms:

- Investigational product: FS VH S/D 500 s-apr

OR

- Control: DuraSeal Dural Sealant

5.6 Blinding

This study will be single-blind (patient), as investigator blinding is not possible due to the visual and physical difference between the 2 treatment regimens. Patients will be kept blinded throughout the study. In addition, the surgeon performing the surgery will remain blinded until intra-operative entry criteria have been confirmed (see Section 5.2).

Otherwise, investigators, surgery personnel, site study personnel, clinical research organisation personnel, and sponsor personnel will not be blinded. Adequate block size will be used to prevent guessing the allocation in the trial and to ensure real blinding. Flexible random block sizes will be also used based on the stratification factors (site and surgical region), eg, relative small block sizes will be used to maintain balance in small strata whereas relative large block sizes will be used in large strata.

5.7 Concomitant Therapy and Prohibited Medications

5.7.1 Concomitant Therapy

The following medications and non-drug therapies are permitted before study entry and during the course of the study:

Medications:

- Prophylactic antibiotics from 1 - 2 days before surgery
- Thrombosis prophylaxis
- Standard use of peri-operative steroids (ie, corticosteroids) is permitted. Chronic steroid use (defined as daily use of corticosteroids for ≥ 8 weeks) for the purposes of reducing the side effects of chemotherapy and/or radiation therapy for cancer is not exclusionary unless the patient is deemed by the investigator to be suffering from steroid toxicity (ie, Cushing's syndrome) manifested by symptoms and signs such as thin skin, striae, easy bruising, muscle atrophy, upper body obesity, severe fatigue, etc.
- Birth control for women of childbearing potential
- Anesthetic drugs and drugs used in the operating room such as induction agents, volatile anaesthetics, nitrous oxide, narcotics, benzodiazepines, paralytics, cardiovascular drugs, antihypertensives, etc.

Non-drug therapies:

- Concomitant medications and non-drug therapies received from 30 days before enrolment until completion/termination will be recorded on the concomitant medications and non-drug therapies eCRFs.
-
- 

5.7.2 Prohibited Medications

The following medications and non-drug therapies are **not** permitted before study entry (surgery) and during the course of the study (for the time specified below):

Medications:

- Chemotherapy from 3 weeks prior to, and 7 days after, surgery
- Investigational product from other clinical trials 30 days before and during the entire study or anticipated in the 60-day Follow-up period.

Non-drug therapies:

- Existing CSF drains, Cushing/Dandy cannulation, or Burr holes with damage to the dura before surgery. CSF drains placed during surgery are allowed.
- Use of implants or grafts made of synthetic materials coming into direct contact with dura during surgery
- Placement of Gliadel Wafers during surgery
- Radiation therapy for the head within 7 days following surgery
- Other FSs or PEG-based sealants, unless used as rescue therapy if the assigned study treatment fails

A patient who has taken any of these medications or received any of these non-drug therapies will be excluded according to exclusion criteria (Sections 4.2.2 and 4.3.2). If this occurs after randomisation, it will be regarded as a protocol violation.

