4.3.2 Exclusion Criteria (Intra-operative)

1. Patient has a gap between durotomy edges of >2 mm after primary dural closure in the judgment of the investigator
2. Patients requiring the use of implants made of synthetic materials coming into direct contact with dura
3. Patient has 2 or more separate dural defects
4. Patients with intersecting durotomy scars in the surgical path from a previous operation that cannot be completely removed by the planned dural resection
5. Placement of Gliadel Wafers
6. Major intra-operative complications that require resuscitation or deviation from the planned surgical procedure
7. Patients in whom application of the Valsalva manoeuver is not found appropriate due to increased safety risk
8. Patients requiring the use of other FSs or PEG-based sealants
9. Patients with any other intra-operative findings identified by the surgeon that may preclude the conduct of the study procedure

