6.13.1 Performing Adverse Events Assessments

During the course of the study, the investigator or designee will routinely monitor and solicit each patient for the occurrence of any AEs, no matter how common they are for a particular patient and regardless of the causality. All AEs (initial, follow-up) will be entered in the eCRF and SAEs (initial, follow-up, upgraded AEs, revisions/amendments) will simultaneously be submitted using a paper SAE Report (SAER) Form.

If a definitive diagnosis has been medically established by the investigator, this diagnosis should then be recorded as the AE. If a definitive diagnosis has not been medically established, the signs and symptoms should then be recorded as the AEs using standard medical terminology, in order to avoid the use of vague, ambiguous, or colloquial expressions.

If a patient experiences an AE, but also additionally a complication of the AE (eg, myocardial infarction with congestive heart failure), both the AE and the additional medical complication should be collected and recorded on CRFs as separate AEs.

Each AE will be evaluated by the investigator for seriousness, severity, and causal relationship to IP/control exposure or study procedure.

For each AE, the outcome (ie, recovering/resolving, recovered/resolved, recovered/resolved with sequelae, not recovered/not resolved, fatal, unknown) and if applicable action taken (ie, none, drug/device withdrawn, not applicable (AE occurred before drug/device application), or unknown) will also be recorded on the AE eCRF. If the severity rating for an ongoing AE changes before the event resolves, the stop date of this AE will be recorded and a new AE report will be entered with the new severity rating.

Deviations from the protocol-specified dosage (including use of more than the maximum 2 allowable applications of IP/control), treatment errors (including incorrect route of administration, use of an incorrect product, and deviations from the protocol-defined dosing and application schedule), failures of expected pharmacological actions, and unexpected therapeutic or clinical benefits will be followed with regards to occurrence of AEs, lack of efficacy, and/or other observations because these events may be reportable to regulatory authorities.

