9.3.2 Per Protocol Set (PPS)

The patients included in the FAS without any major protocol deviations, which could impact the primary endpoint assessment, will be included in the Per Protocol Set (PPS). The PPS is defined by the following:

- Patients who meet all inclusion criteria and do not meet any exclusion criteria.
 - Patients who are randomised and treated according to the randomisation scheme.
 - Patients with no major protocol deviations which could impact the primary endpoint assessment.
 - Availability of primary endpoint assessment.
-
- 

Furthermore, any other major protocol violations, such as serious unforeseen violations deemed to invalidate the data and affect the conclusions of the study, will lead to the exclusion of patients from the PPS.

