6.3 Protocol Deviations

Protocol deviations will be classified as minor or major deviations and reviewed at a data review meeting. Subjects with any major deviation that may impact the primary efficacy parameter will be excluded from the per-protocol analysis set, including the following:

- Violations inclusion and/or exclusion criteria (pre and/or intra-operative assessment)
- Use of prohibited medication known to influence the primary endpoint
- Randomization or treatment errors
- Improper administration of study product
- Improper assessment of the primary endpoint

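### A patient already recorded as an intra-operative failure could be dropped from the primary per-protocol set because of what was done afterwards to treat the failure

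*Protocol*

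**What the plan says.** **Rescue.** Protocol 5.3.5 leaves rescue of a leak that persists despite treatment to the surgeon, "including use of other sealants, dural patches, etc". It rules out only further use of the study product or the control, and does not restrict the material of a patch.

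**Prohibited therapies.** The non-drug list in Protocol 5.7.2 includes "Use of implants or grafts made of synthetic materials coming into direct contact with dura during surgery", with no exception for rescue. The same list does carry a rescue exception, but only on one item: "Other FSs or PEG-based sealants, unless used as rescue therapy if the assigned study treatment fails". On any prohibited item it adds: "If this occurs after randomisation, it will be regarded as a protocol violation".

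**Analysis sets.** Protocol 9.4 and SAP 6.2 and 10.1 make the PPS primary and the full analysis set (FAS) supportive. Protocol 9.3.2 and SAP 6.3 remove patients with a major deviation that could affect the primary endpoint. SAP 6.3 names, among other grounds, "Use of prohibited medication known to influence the primary endpoint", treatment errors and incorrect administration of the product. A data review meeting reviews the classification of deviations as major or minor. Under Protocol 5.6, sponsor and CRO personnel are not blinded.

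Neither document says that a patient who failed intra-operatively and was then rescued stays in the PPS as a failure.

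**The concern.** Rescue is given only when the seal has failed. Any deviation that consists of the rescue itself therefore occurs only in patients who have already failed the primary endpoint. If such a deviation leads to PPS exclusion, the exclusion depends on the outcome and can only remove failures. Where both arms lose a similar share of their failures, the arm with more failures loses more patients and the observed difference shrinks towards zero, even if surgeons behave identically in both arms. The decision would then rest on how a review meeting with access to treatment and outcome classifies a few known failures. The FAS keeps these patients, but it does not decide the trial.

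**Working it through.** **1. The passages side by side.**

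| Step taken after a recorded intra-operative failure | Protocol 5.3.5 | Protocol 5.7.2 | Possible PPS ground in SAP 6.3 |
|---|---|---|---|
| Other fibrin or PEG sealant | permitted | exempt as rescue | none |
| Non-synthetic patch | permitted | not listed | none |
| Synthetic patch touching dura | permitted | prohibited, no exemption | prohibited therapy |
| Further application, or the other study product | not permitted | not the source of the problem | treatment error or incorrect administration |

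The two sections contradict each other only in the third row. The fourth row contains no contradiction, but it leads to the same place: a deviation that follows the failure and is a possible reason for exclusion.

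**2. The plan's own figures.** The control rate is 90.6% (Protocol 9.2.1), the margin 10 points, and the evaluable sample 202, or 101 per arm (Protocol 9.2). The assumed fibrin sealant (FS) rate is blacked out, so 202 cannot be reproduced independently. It is attainable: with the unpooled formula and an FS rate of 91.8%, n per arm = 7.849 × (0.906×0.094 + 0.918×0.082) / 0.112² = 100.4, rounded up to 101. The randomised number is consistent with it: 224 × 0.9 = 201.6. The plan thus allows for about 224 − 202 = 22 PPS exclusions.

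**3. Effect on the expected difference.** If a share s of failures is dropped, the expected PPS success rate is p / (1 − (1 − p)s). At the non-inferiority boundary FS is 90.6% − 10 = 80.6%.

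- s = 10%: 0.806/0.9806 − 0.906/0.9906 = 0.8220 − 0.9146 = −9.3 points.
- s = 20%: 0.806/0.9612 − 0.906/0.9812 = 0.8385 − 0.9234 = −8.5 points.

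**4. Effect on the error rate.** The decision rule is that of SAP 10.1 (lower 95% bound above −10%), approximated by an unadjusted Wald interval with the interim ignored; 400,000 simulated trials with 101 per arm. The shares dropped are assumptions.

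| Failures dropped | Patients dropped (FS / DuraSeal) | Expected difference | False non-inferiority |
|---|---|---|---|
| none | 0 / 0 | −10.0 | 2.8% |
| 10%, both arms | 2.0 / 0.9 | −9.3 | 4.1% |
| 20%, both arms | 3.9 / 1.9 | −8.5 | 6.0% |
| 10%, FS only | 2.0 / 0 | −8.4 | 5.8% |
| 10%, DuraSeal only | 0 / 0.9 | −10.9 | 1.9% |

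With the control at 85% (75% against 85%), dropping 10% in both arms moves the error from 2.7% to 3.5%.

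**5. A single trial.** Take 11 FS and 9 DuraSeal failures out of 101 each. The difference is 90/101 − 92/101 = −2.0 points, with standard error 4.20 points and lower bound −10.2%: non-inferiority is not shown. Drop two FS failures and one DuraSeal failure. The difference becomes 90/99 − 92/100 = −1.1 points, with standard error 3.96 points and lower bound −8.9%: non-inferiority is shown. Three patients decide the result, against about 22 exclusions allowed for.

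**The case against.** The best counter-argument is that these patients would stay in on a sensible reading. Protocol 5.7.2 speaks of a violation, not a major one. Protocol 9.3.2 and SAP 6.3 require a deviation that could affect the primary endpoint, and rescue after the final Valsalva test cannot change a failure already recorded. SAP 6.3 also speaks of medication, while 5.7.2 lists synthetic grafts under non-drug therapies. This stands to the extent that exclusion is not automatic. It does not close the gap, because neither document states that reading. The composite also covers leakage to day 30 (+3), which a patch could plausibly influence, so a reviewer could in good faith call it relevant.

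A reader might infer three stronger things that the documents do not support.

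- *That rescued patients in general become violators.* They do not: other fibrin and PEG sealants used as rescue are expressly exempt, and non-synthetic patches are not prohibited.
- *That rescue makes the patient retrospectively ineligible*, through "Patients requiring the use of other FSs or PEG-based sealants" or the matching criterion on synthetic implants in Protocol 4.3.2, together with the PPS condition "Patients who meet all inclusion criteria and do not meet any exclusion criteria". Those are entry criteria, checked before the assigned treatment is revealed and applied. Later rescue does not breach them.
- *That the bias is large and always favours FS.* The direction reverses when mainly DuraSeal failures are dropped. The simulated shares apply to all failures, yet a patient whose first leak is post-operative cannot have been rescued for an intra-operative one, so large shares lack support.

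On further applications, Protocol 6.13.1 ("including use of more than the maximum 2 allowable applications of IP/control") concerns safety follow-up and reporting, not analysis sets. The route to exclusion there is SAP 6.3 alone.

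**Conclusion.** The plan is wrong as written in two respects. Sections 5.3.5 and 5.7.2 conflict on synthetic patches used as rescue. The PPS rules also leave open whether a recorded intra-operative failure can be removed because of a later deviation. The size is illustrative: false non-inferiority goes from 2.8% to 4.1% if 10% of failures are dropped in both arms and to 6.0% at 20%, and down to 1.9% if 10% of DuraSeal failures alone are dropped. These figures assume 90.6% against 80.6%, 101 per arm and an unadjusted Wald interval (which itself explains a baseline of 2.8% rather than 2.5%), with no interim look. The documents do not give the split between intra- and post-operative failures, the rescue materials used, or how many such cases would be judged major. The true effect could be nil. What makes the point worth correcting is that two or three patients can decide the result and the classification is left to an unblinded judgement.

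**What to change.** In Protocol 9.3.2 and SAP 6.3, state that a patient with a CSF leak at the final intra-operative assessment, meaning the one after up to two applications, stays in the PPS as a failure, and that no deviation occurring after that assessment is a reason for PPS exclusion. Grounds that arise before or at the assessment would be handled as now. The rule should be in place before the data review meeting, since a choice made there would be made with outcomes known.

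Separately, Protocol 5.3.5 and 5.7.2 must be reconciled on rescue materials. No view is taken here on which material should be allowed. The PPS sentence works whichever way that is settled.

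The cost is wording only. Rescue use and material are already recorded (Protocol 5.3.5 and 7.4), and the time of rescue is in the SAP 9.3 listing. The one downside is that PPS success rates may look slightly lower.

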5.8 Restrictions

5.8.1 Fluid and Food Intake

No special requirements on fluid and food intake are necessary, other than the standard procedure (ie, no food or liquids after 12 am on the day of surgery).

5.8.2 Patient Activity Restrictions

No special requirements on patient activity are necessary, other than those imposed by the investigator or as per standard post-operative procedure.

5.9 Treatment Compliance

Not applicable.

5.10 Packaging and Labeling

The FS VH S/D 500 s-apr and DuraSeal Dural Sealant batches used in this study will be labeled with the contents, storage instructions, and expiry date, along with other information according to the valid regulatory requirements for clinical trials. The study product is delivered in cardboard boxes.

5.11 Storage and Accountability

The shelf life of FS VH S/D 500 s-apr (frozen) is 24 months, provided that the product is shipped and stored at or below -4°F (-20°C). The cooling chain must be maintained without interruption until application. The unopened product, thawed in an incubator at 98.6°F (37°C), may be stored at 98.6°F (37°C) for up to 4 hours. If the solution is not used within 4 hours after thawing, FS VH S/D 500 s-apr must be discarded. Do not refrigerate or re-freeze. The product must not be used after the expiration date indicated on the label. For additional information on these issues, please see the SmPC.¹⁹

The shelf life of DuraSeal Dural Sealant is 12 months, provided that the product is shipped and stored below 77°F (25°C). DuraSeal Dural Sealant must be used within 1 hour of preparation.²⁷

The investigator will ensure that the IP is stored as specified above and that the storage area is secured, with access limited to authorised study personnel. The investigator will maintain records that the IP was received, including the date received, drug identity code, date of manufacture or expiration date, amount received, and outcome of the product. The IPs must be dispensed only at the study site. Records will be maintained that includes the patient identification code (PIC), dispensation date, and amount dispensed. All remaining partially used and/or unused IP will be destroyed with the permission of the sponsor in accordance with applicable laws and study site procedures for waste of biological human origin. If the IP is to be destroyed, the investigator will provide documentation in accordance with sponsor's specifications.

6. STUDY PROCEDURES

6.1 Informed Consent

The investigator or designated personnel must explain the study and the implications of participation (e.g., objectives, methods, anticipated benefits, and possible risks) to potential patients according to local regulations prior to any trial related activity. Patients will be informed that their participation is voluntary and that they may withdraw from the study at any time. They will be informed that choosing not to participate or to withdraw from the study will not have an impact on the care the patient will receive for the treatment of his/her disease. In case the patient is unable to read and write, an impartial witness must confirm the informed consent.

The patient will be given sufficient time to read the informed consent form (ICF) and to ask additional questions. After this explanation and before entry in the study, consent should be appropriately recorded by means of the patient's personally dated signature (or, if applicable, by the signature of an independent witness who certifies the patient's consent in writing) and by the investigator's signature. After having obtained the consent, a copy of the signed and dated informed consent must be given to the patient.

Any patient who provides informed consent and meets the general inclusion/exclusion criteria is considered enrolled into the study.

